4.1.1.1. The von Hippel-Lindau Tumor Suppressor Gene

A study of VHL kindreds at the National Cancer Institute (NCI) led to identification of the *VHL* gene (Latif et al, 1993). The *VHL* gene is a classical tumor suppressor gene and tumorigenesis due to VHL inactivation conforms to Knudson's 'two-hit' hypothesis (Knudson, 1986). The gene has 3 exons that encode the VHL protein (Latif et al, 1993).

While VHL mutations were initially identified in the germline of patients with VHL disease, inactivation of the gene by somatic mutation or promoter hypermethylation has also been described in a high proportion of sporadic ccRCC. The function of VHL proteins and the biochemical consequences of VHL gene inactivation have been studied extensively. Von Hippel-Lindau protein forms a complex with other cellular proteins including elongins B and C, and Cullin 2 (Pause et al, 1997). This complex plays an important role in the degradation of cellular proteins via the ubiquitin pathway. Inactivation of the VHL gene consequently leads to accumulation of proteins targeted for degradation through this pathway. These proteins include the alpha subunits of a group of transcriptionally active proteins called the hypoxia inducible factors (HIFs) (Maxwell et al, 1999). Accumulation of HIFs results in overexpression of several genes including those encoding vascular endothelial growth factor A (VEGFA), glucose transporter 1 (GLUT1), transforming growth factor alpha (TGF-α), platelet-derived growth factor (PDGF), cyclin D1 (CCND1) and erythropoietin (EPO) (Linehan et al, 2001; Linehan et al, 2002; Linehan et al, 1995; Clifford and Maher, 2001). VEGFA is an important regulator of tumor angiogenesis that supports tumor growth and progression. VEGFA exerts its activity through several receptor tyrosine kinases expressed on endothelial cells, chief among them being the fms-like tyrosine kinase-1/vascular endothelial growth factor receptor 1 (Flt-1/VEGFR1) and the kinase insert domain containing receptor/vascular endothelial growth factor receptor 2 (KDR/VEGFR2) (Ferrara, 2001). In addition to promoting angiogenesis in the tumor microenvironment, VHL

Peloton Therapeutics, Inc. CONFIDENTIAL

inactivation can also directly promote tumor growth via the autocrine and paracrine effects of transforming growth factor alpha (TGF- α), and PDGF, which act through receptor tyrosine kinases such as the epidermal growth factor receptor (EGFR, a receptor for TGF- α) expressed on tumor cell surface. Thus, VHL deficiency initiates a series of downstream events that promote tumor progression.

4.1.1.2. HIF-2α

A strong connection has been established among the histologic features of ccRCC, mutations in the VHL tumor suppressor gene and the subsequent activation of HIF-2 α transcriptional activity (Shen and Kaelin, 2013). More than 90% of sporadic ccRCC tumors have defective or deficient VHL function through deletion, mutation, or hypermethylation of the VHL gene (Sato et al, 2013). Although both HIF-1 α and HIF-2 α are stabilized upon VHL loss, a greater role has been ascribed to HIF-2 α in the pathobiology of ccRCC. As much as 40% of sporadic ccRCC have reduced copy number and expression of HIF-1 α , and HIF-2 α alone is sufficient to support the growth of ccRCC mouse xenografts (Sato et al, 2013, Kondo et al, 2002). In this setting, HIF-2 α will accumulate, even under normoxic conditions, and drive the expression of genes associated with tumor growth. Preclinical studies showed that HIF- 2α depletion or pharmacologic antagonism is sufficient to inhibit ccRCC tumor growth (Kondo et al, 2002; Wallace et al, 2016; Chen et al, 2016; Cho et al, 2016). HIF- 2α has therefore been established as an oncogenic driver in ccRCC, where VHL deficiency is the underlying genomic alteration. In VHL disease, renal tumors are of clear cell histology (Lund et al, 1994; Poston et al, 1995). Further, expression of HIF-2 α has been found to correlate with disease development in renal cancer, as well as in paraganglioma and pheochromocytoma associated with VHL disease (Mandriota et al, 2002; Pollard et al, 2006). Thus, HIF-2 α stabilization and activation appears to be common to the spectrum of neoplasms associated with VHL deficiency, suggesting that HIF-2 α may be a major driver of the disease pathology. Inhibition of this transcription factor is a novel approach that could lead to a significant new treatment option for patients with VHL disease.

4.1.2. PT2385

PT2385 is a first-in-class small molecule inhibitor of HIF-2 α , which impairs hypoxic signaling in cancer cells.

4.1.2.1. Pharmacologic Activity

PT2385 is a potent and selective inhibitor both in vitro and in vivo and has been shown to inhibit signaling by disrupting the formation of the HIF-2 α : aryl hydrocarbon receptor nuclear translocator (ARNT) heterodimer in cells. Thus, in tumors where HIF-2 α is activated, PT2385 blocks the transcription of several genes involved in oncogenesis,

Additionally, PT2385 has demonstrated anti-tumor activity in **Constant and Second Seco**

rapid (10 mg/kg twice daily versus 20 mg/kg once daily) with twice daily dosing. PT2385 has shown no activity (up to 10 μ M) against other Per-ARNT-Sim-B (PAS-B) domain-containing proteins or against a large panel of receptors, ion channels, and kinases. Studies to date have not revealed any cardiovascular, central nervous system or respiratory safety pharmacology issues with PT2385 treatment in vitro or in vivo. Refer to the Investigator's Brochure for additional information.

Preclinical studies demonstrate that PT2385 is a potent and selective inhibitor of HIF-2 α . Additionally, they demonstrate that inhibition of HIF-2 α with PT2385 is efficacious in the treatment of sporadic ccRCC tumors with VHL mutations in mouse models. Although there are no mouse models for evaluating PT2385 in VHL disease pathologies, the preclinical and clinical data for PT2385 in sporadic ccRCC support its testing in ccRCC associated with VHL disease, given the identical histologic and molecular characteristics of these 2 types of renal cancer.

4.1.2.2. Pharmacokinetic Data

Absorption of PT2385 following administration of an oral dose was rapid in all species, with the time at which maximum concentrations occurred (t_{max}) between 0.5 and 2 hours in most preclinical studies. Oral bioavailability was high in mice and dogs (95% and 89%, respectively), moderate in rats (41%), and low in monkeys (16%) following a single oral dose.

Overall, exposure to PT2385 in rats and dogs was somewhat dose proportional up to doses of 300 mg/kg, was less than dose proportional up to 450 or 600 mg/kg, and showed little to no increase with doses of 1000 mg/kg. There was no consistent evidence of a sex difference in PT2385 exposure in rats and dogs.

PT2385 showed time-dependent pharmacokinetics following 28-day twice-daily dosing in rat and dog toxicokinetic (TK) studies. The ratio of Day 28/Day 1 PT2385 AUC_{0-tau} (area under the plasma concentration curve from time over 1 dose interval) decreased as dose increased, which was more severe in dogs than in rats.

Tissue distribution after administration of a single oral dose of PT2385 was evaluated in rats. The highest concentration of PT2385 was observed in the liver followed by the heart, kidney lung, plasma and brain. Permeability across the blood-brain barrier was also demonstrated after administration of repeat doses in mice and in rats, where concentrations of PT2385 were similar in plasma and brain tissue. The in vitro plasma protein binding of PT2385 was moderate and ranged from 64% to 82% across species (82% for human plasma protein).

In vitro, the primary biotransformation route of PT2385 was direct conjugation to form a glucuronide conjugate (PT2639), oxidative metabolism to M+16, oxidative defluorination and subsequent conjugation to glucuronides. No human specific metabolite was found. Enzyme phenotyping results suggested PT2385 was primarily metabolized via UGT2B17, UGT2B7, UGT2B15, CYP2C19 and CYP3A4 in human.

PT2385 is not a potent inhibitor for CYP1A2, CYP2B6, CYP2C8, CYP2C9, CYP2C19, CYP2D6 and CYP3A4 (IC50 > 8.8 μ g/mL). It is unlikely to significantly inhibit these CYPs at the clinically relevant PT2385 concentrations (maximum peak concentration [C_{max}] ~ 3.14 μ g/mL).

PT2385 induced concentration-dependent increases in CYP2B6 and CYP3A4 mRNA in cultured human hepatocytes. Simcyp physiologically-based pharmacokinetic (PBPK) model simulations indicate a weak-to-moderate CYP3A4 substrate midazolam drug-drug interaction (DDI) (~50% reduction in midazolam AUC) at the clinical relevant PT2385 doses. A qualitative assessment of the DDI liability of sunitinib, cabozantinib, and axitinib when co-administered with PT2385 was performed using literature data; the expected DDI effects with these kinase inhibitors are smaller than the effect predicted for midazolam. Simulations also indicate that PT2385 is a weak CYP2B6 inducer (< 11% AUC reduction for CYP2B6 substrate bupropion at the clinical relevant PT2385 doses).

4.1.2.3. Toxicity

The nonclinical toxicology studies were designed to assess the toxicity potential of PT2385, with appropriate TK monitoring. Exploratory studies assessed the tolerability of PT2385 in mice, rats and dogs. Based on the findings that the putative metabolites predicted in humans were also observed in rat and dog hepatocytes, and oral administration of PT2385 to these species achieved good bioavailability, the rat and dog were selected for definitive toxicity studies. The tolerability studies demonstrated a reversible dose-responsive effect on the red blood cell compartment. This effect encompassed the total red blood cell count, hemoglobin concentration and hematocrit with reductions in all indices. The immature red cell fraction, as noted by the reticulocyte count, was also impacted in a reversible manner.

The definitive toxicity studies were designed to assess the safety and reversibility of effects from PT2385 administration. Twice-daily PT2385 was administered orally for 28 days to rats and dogs in GLP studies. Overall results demonstrated PT2385 to be clinically well tolerated for up to 28 days with twice-daily administration. There were no deaths in either toxicity study. A recoverable mild anemia was identified in both studies, similar to the pilot experiments. In both the rat and dog studies, a hepatocellular hypertrophy was observed histologically, indicative of an adaptive response. This effect was completely reversible following removal of the test item. Based on metabolism studies examining CYP3A4 and CYP2B6 mRNA induction in human hepatocytes, this effect may relate to induction of hepatic enzymes. This histological finding corresponded with a dose-dependent increase in liver weights and a reduction in plasma concentrations from Day 1 to Day 28 in both the rat and dog.

From the 28-day studies, the only identified target organs for toxicity were the testes and epididymis in male rats. The effect was dose responsive on the seminiferous tubule epithelium and ranged from mild to marked in severity. Following the recovery period, the testes did not demonstrate recovery of effect, while the epididymis demonstrated a partial recovery of effect. Possibly, a longer recovery period that captured the entire cycle of spermatogenesis (63 days) could have afforded complete recovery. No target organs were identified in female rats.

PT2385 did not have a consistent effect on the testes of male dogs, however sporadic effects were noted. These changes were considered related to the young age of the animals. No target organs were identified in female dogs.

Assessment of genotoxicity included in vitro bacterial mutagenicity and chromosomal aberration assays. Both assays were conducted with and without metabolic activation and both yielded negative results with PT2385.

PT2385 will be administered orally at a dosage of 800 mg twice daily. This dose was identified in the initial study of PT2385 in humans, a Phase 1 study in patients with advanced clear cell renal cell carcinoma, as the recommended Phase 2 dose (RP2D) (Courtney et al, 2016). The starting dose in that study was 100 mg twice daily based on the identification of the mid dose, 200 mg/kg/day, as the highest non-severely toxic dose because of associated minimal to moderate changes in the testes and epididymis that were not completely reversible.

4.1.2.4. Clinical Studies

PT2385 has not previously been studied in patients with VHL disease. Clinical studies of PT2385 in ccRCC are ongoing. Under Protocol PT2385-101, patients with advanced ccRCC who had been treated with at least 1 prior treatment with a VEGF inhibitor were treated with PT2385 twice daily in a 3+3 Phase 1 design to determine the maximum tolerated dose (MTD)/RP2D and to evaluate safety, PK, and pharmacodynamics (PD). The 26 patients enrolled in the dose-escalation portion received PT2385 at oral dosages of 100 to 1800 mg twice daily. No dose limiting toxicities (DLTs) were observed at any dose level. Exposure generally increased with dose up to the 800 mg dose, without a further increase from 800 to 1800 mg. At 800 mg, PT2385 was rapidly absorbed with a C_{max} of 3.14 µg/mL and a $t_{1/2}$ of 17 hours. The targeted C_{min} of 280 ng/mL was exceeded in the majority of patients receiving a twice daily dose of \geq 800 mg. Circulating plasma levels of EPO rapidly decreased within 24 hours in most patients receiving \geq 800 mg and remained suppressed during the 16-week sampling period. Based on safety, PK, and EPO PD data, the RP2D has been defined as oral 800 mg twice daily. An additional 25 patients were enrolled in an expansion cohort at the RP2D. As of August 15, 2016, the most common adverse events (AEs) of any severity have been anemia, peripheral edema, and fatigue. One patient had a complete response (CR), 4 patients had a partial response (PR), and 16 patients had stable disease (SD) for more than 16 weeks. PT2385 administration was safe and well tolerated, and has demonstrated early evidence of clinical activity in these heavily pre-treated patients with advanced ccRCC (Courtney et al, 2016).

A Phase 1 food effect study of PT2385 was conducted in healthy female volunteers. The most common AEs were headache, injection site bruising, and nausea. The presence of food had a mild effect (19% to 37% increase) on the exposure to PT2385 in this study; little to no effect was observed in exposure to PT2639, the major metabolite, in the presence of food.

4.2. Study Rationale

This study is part of the clinical program to investigate PT2385 as a treatment for VHL disease-associated ccRCC.

Patients affected with VHL, a rare hereditary cancer syndrome, are at risk to develop ccRCC as well as pheochromocytomas; pancreatic cysts; neuroendocrine tumors; hemangioblastomas of the brain and spinal cord; retinal angiomas; inner ear endolymphatic sac tumors; and epididymal and broad ligament cystadenomas. The current treatment

paradigm is based upon frequent monitoring and surgery, as no therapies are approved for treatment of VHL disease. Although effective in limiting metastatic disease spread, surgery is associated with significant morbidity, particularly in patients undergoing multiple surgical interventions. Development of systemic options that can delay or obviate the need for surgery is, therefore, desirable.

Patients enrolled in this present study will be treated with oral PT2385, 800 mg twice daily. Overall response rates in this patient population will provide insight into the efficacy of PT2385 as reduction in tumor size relates to preclusion or delay of surgery-associated morbidity and mortality.

5. TRIAL OBJECTIVES AND PURPOSE

This open-label Phase 2 study will evaluate the efficacy, safety, tolerability, PK, and PD of PT2385 for the treatment of VHL disease-associated ccRCC.

5.1. **Primary Objective**

To assess overall response rate (ORR) of von Hippel-Lindau (VHL) disease-associated ccRCC tumors in VHL patients treated with PT2385 as determined by Response Evaluation Criteria in Solid Tumors Version 1.1 (RECIST 1.1, Appendix 3); ORR is defined as the proportion of patients with a best confirmed response of complete response (CR) or partial response (PR).

5.2. Secondary Objectives

- To evaluate progression-free survival (PFS) in patients with VHL disease-associated ccRCC tumors treated with PT2385
- To evaluate duration of response (DOR) and time to response (TTR) in patients with VHL disease-associated ccRCC tumors treated with PT2385 who achieve a PR or better as determined by RECIST 1.1
- To study the effect of treatment with PT2385 on VHL disease-associated non-ccRCC tumors by modifying RECIST 1.1 criteria to assess tumors in individual organ systems independently rather than collectively
- To study the safety and tolerability of PT2385
- To study the pharmacokinetics (PK) of PT2385

5.3. Exploratory Objectives

• To evaluate changes in pharmacodynamic (PD) markers (e.g., serum EPO) in patients treated with PT2385

6. INVESTIGATIONAL PLAN

6.1. Overall Study Design

This open-label Phase 2 study will evaluate the efficacy, safety, PK, and PD of PT2385 in patients with VHL disease who have at least 1 measurable VHL disease-associated ccRCC tumor (as defined by RECIST 1.1). PT2385 will be administered orally at a dosage of 800 mg twice daily. Treatment will be continuous; the drug will be administered twice daily every day. Patients will be entered in the study after meeting all inclusion criteria and no exclusion criteria. This study will be conducted with a 2-stage design, which allows for an early assessment of futility. A response will be defined as either a PR or CR occurring at any time after initiation of treatment, based on assessment of ccRCC tumors. All responses must be confirmed after the initial response is documented. Changes in VHL disease-associated non-ccRCC tumors will also be evaluated independently by modifying RECIST 1.1 criteria to assess tumors in individual organ systems independently rather than collectively.

Twenty-five patients will be enrolled during the first stage. A Data Monitoring Committee (DMC) will perform the safety review for the first 6 patients and the futility analysis for Stage 1 of the study. The DMC will review safety and any treatment-limiting toxicities to confirm whether the study should continue to enroll or if modifications to the protocol are needed. The DMC will review the response data from the first 25 patients to determine if at least 3 patients have a confirmed PR or better in ccRCC tumors and that the threshold for opening Stage 2 has been met. Treatment-limiting toxicities will be assessed according to Section 6.4. Study termination criteria are presented in Section 6.5.

In the second stage of the study, 25 additional patients will be enrolled, to a maximum accrual of 50 patients.

Patients will undergo clinical and laboratory evaluations every 2 weeks for the first 4 weeks and then every 4 weeks (i.e., 28 days) according to the Schedule of Events. Patients will be evaluated radiologically for evidence of response or progression approximately 12 weeks after initiation of treatment and every 12 weeks thereafter while continuing in the study. Patients with evidence of stable disease or disease response, i.e., CR or PR, will continue to receive treatment in the absence of serious toxicity. Patients who demonstrate disease progression of their ccRCC tumors at any time will be withdrawn from study treatment.

Patients who need surgical intervention for VHL-disease associated non-ccRCC tumors, and who do not meet the RECIST 1.1 criteria for progression of the ccRCC tumors, while participating in the study, may be allowed to resume study drug administration, as long as study drug has been withheld no more than 8 weeks, and there is no progression of ccRCC tumors. Patients with non-ccRCC tumors that meet the RECIST 1.1 criteria for progression will be withdrawn from study treatment.

Patients who undergo resection of non-renal VHL disease-associated lesions, and who do not meet the RECIST 1.1 criteria for progression of those lesions, may resume treatment with PT2385 once the surgical incisions have adequately healed, and if in the opinion of the Principal Investigator, the patient is likely to experience clinical benefit.

Patients who discontinue from study treatment for any reason will be followed every 6 months either by telephone or office visit to determine their medical history, surgical history,

disease status, and survival status. These patients will be followed for up to 3 years following the completion of enrollment in the study or until the patient either withdraws consent or dies.

6.2. Number of Patients

A total of 50 patients will be enrolled in the study: 25 patients will be enrolled in the first stage; 25 patients will be enrolled in the second stage.

6.3. Treatment Assignment

After meeting all inclusion and no exclusion criteria, enrolled patients will be assigned to treatment with open-label PT2385. The treatment will be administered orally at a dosage of 800 mg twice daily (four 200 mg PT2385 tablets twice daily).

6.4. Dose Adjustment Criteria

For patients who experience a treatment-limiting toxicity and require dose modification, the guidelines in Table 1 will be used to determine the dose modification required. If the Investigator believes that the guidelines should not apply, he/she will contact the Sponsor's medical monitor to discuss the circumstances and the appropriate dose modification.

Patients requiring surgical intervention for non-renal lesions during the course of the study should have study drug treatment interrupted. Study drug may be restarted when the surgical incision has adequately healed, provided there is no evidence of progression of ccRCC, and study drug interruption has been for no more than 8 weeks. Patients with non-renal lesions that meet the RECIST 1.1 criteria for progression will be withdrawn from study treatment.

Patients requiring study drug interruption for more than 3 weeks will be withdrawn from study treatment, except in the instance of interruption for surgery as noted above.

Treatment-limiting toxicity in the first 6 patients will be defined as any of the following events occurring in the first 28 days of treatment, graded using the National Cancer Institute Common Terminology Criteria for Adverse Events Version 4.03 (NCI CTCAE 4.03):

- Hematologic
 - Febrile neutropenia (absolute neutrophil count < 1,000/ μ L plus body temperature \geq 38.5°C)
 - Grade 4 neutropenia lasting for > 5 days (in the absence of growth factor support)
 - Grade 3 thrombocytopenia with bleeding
 - Grade 4 thrombocytopenia
 - Grade 4 anemia unexplained by underlying disease
- Gastrointestinal
 - Grade 3 or 4 nausea, vomiting, or diarrhea that persists for > 48 hours despite optimal antiemetic or antidiarrheal treatment

- Hepatic
 - Grade 3 or greater increase in transaminase levels, if confirmed upon repeat testing within 48 hours
 - Grade 3 or 4 increase in transaminase levels if accompanied by a Grade 2 increase in bilirubin level and an alkaline phosphatase level > 2 × upper limit of normal (ULN)
- Other
 - Any other study drug-related Grade 3 or 4 non-hematologic toxicity, except for Grade 3 asymptomatic hypoxia unless considered clinically significant by the Investigator
 - Any study drug-related Grade 3 or 4 laboratory toxicity that does not resolve within 48 hours and is considered clinically significant by the Investigator.

Table 1Guidelines for Dose Modification

Toxicity	Occurrence	Action
Hematologic • ANC < $1,000/\mu$ L + body temperature $\ge 38.5^{\circ}$ C, or	1 st	Hold study drug. Once toxicity has resolved to $<$ Gr 2 or baseline, restart PT2385 at a 25% reduction of the assigned dose.
 Gr 4 neutropenia for > 5 days, or Gr 3 thrombocytopenia with bleeding, or 	2 nd	Hold study drug. Once toxicity has resolved to $<$ Gr 2 or baseline, restart PT2385 at a 50% reduction of the assigned dose
 Gr 4 thrombocytopenia, or Gr 4 anemia unexplained by underlying disease 	3 rd	Discontinue PT2385.
 Gastrointestinal Gr 3 or 4 nausea, vomiting, or diarrhea if persistent for > 48 hours despite optimal antiemetic or antidiarrheal therapy 	1 st	Hold study drug. Once toxicity has resolved to $<$ Gr 2 or baseline, restart PT2385 at a 25% reduction of the assigned dose.
	2 nd	Hold study drug. Once toxicity has resolved to $<$ Gr 2 or baseline, restart PT2385 at a 50% reduction of the assigned dose
	3 rd	Discontinue PT2385
 Hepatic ≥ Gr 3 increase in transaminase levels, if confirmed upon repeat testing within 48 hours, or 	1 st	Discontinue PT2385
• Gr 3 or 4 increase in transaminase levels if accompanied by a Gr 2 increase in bilirubin level and an alkaline phosphatase level $< 2 \times ULN$		

Toxicity	Occurrence	Action
Other • Any other Gr 3 toxicity, with the exception of Gr 3 cardiovascular, vascular or thrombotic events and Gr 3 asymptomatic hypoxia unless considered clinically significant by the Investigator	1 st	Hold study drug. Once toxicity has resolved to $<$ Gr 2 or baseline, restart PT2385 at a 25% reduction of the assigned dose.
	2 nd	Hold study drug. Once toxicity has resolved to $<$ Gr 2 or baseline, restart PT2385 at a 50% reduction of the assigned dose
	3 rd	Discontinue PT2385
Other	1st	Discontinue PT2385
• Any study drug-related Gr 3 cardiovascular, vascular or thrombotic events		
• Any other study drug-related Gr 4 non- hematologic toxicity		
• Any study drug-related Gr 3 or 4 laboratory toxicity that does not resolve within 48 hours and is considered clinically significant by the Investigator		

ANC = absolute neutrophil count; Gr = Grade; ULN = upper limit of normal.

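### The combined hepatic criterion has opposite ALP signs in Section 6.4 and Table 1, and Table 1 gives two actions for drug-related, clinically significant Grade 3 laboratory toxicity unresolved at 48 hours

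*Combined protocol and SAP*

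**What the plan says.** Section 6.4 of the protocol does two jobs. First, it lists the events that count toward the early safety rule: "Treatment-limiting toxicity in the first 6 patients will be defined as any of the following events occurring in the first 28 days of treatment". Section 6.5 stops or modifies the study if more than 2 of those 6 patients have such an event. Second, it refers to Table 1 for action: "the guidelines in Table 1 will be used to determine the dose modification required".

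**Combined hepatic criterion.** In the Section 6.4 list, a Grade 3 or 4 transaminase rise counts if it is "accompanied by a Grade 2 increase in bilirubin level and an alkaline phosphatase level > 2 × upper limit of normal (ULN". In the hepatic row of Table 1, where the action is discontinuation at first occurrence, the same criterion reads "increase in bilirubin level and an alkaline phosphatase level $< 2" × ULN (the dollar sign is a by-product of text extraction). The other hepatic criterion, a transaminase rise of Grade 3 or more confirmed within 48 hours, is the same in both places.

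**Grade 3 laboratory toxicity.** One Table 1 row, called the general Grade 3 row below, covers "Any other Gr 3 toxicity, with the exception of Gr 3 cardiovascular, vascular or thrombotic events"; it also excepts asymptomatic hypoxia unless clinically significant. Its first-occurrence action is to hold and, after recovery to below Grade 2 or baseline, "restart PT2385 at a 25% reduction of the assigned dose". The last bullet of Table 1 requires discontinuation at first occurrence for a Grade 3 or 4 laboratory toxicity that is drug-related, unresolved at 48 hours and judged clinically significant. The hematologic row (hold and reduce) names Grade 4 anemia but not Grade 3 anemia. Section 12.1.7.1 places hemoglobin among the laboratory assessments.

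**The concern.** The two ALP conditions exclude each other. As printed, a patient can have a listed hepatic toxicity and miss the hepatic row that sets its action; the mirror-image patient is discontinued for a pattern outside the listed combined criterion.

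The second problem does not depend on that sign. For one defined class of Grade 3 laboratory events, Table 1 supports two actions. Both stop the drug at once. They differ on whether a recovered patient may restart at a reduced dose or never. Two investigators could each follow the table and treat the same patient differently. Anemia is the natural example, because it was among the most common adverse events in the Phase 1 study (Section 4.1.2.4) and was seen in both 28-day animal studies (Section 4.1.2.3).

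**Working it through.** **1. What the ALP sign changes in dosing.** Take a Grade 3 or 4 transaminase rise with Grade 2 bilirubin and ALP above 2 × ULN, and read Table 1 as printed (ALP below 2 × ULN).

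- Confirmed within 48 hours: discontinue under the first hepatic bullet, whatever the ALP.
- Grade 4 and drug-related: discontinue under the bullet for drug-related Grade 4 non-hematologic toxicity.
- Grade 3, drug-related, clinically significant and unresolved at 48 hours: caught by the last discontinuation bullet, subject to the overlap in step 3.
- Grade 3, unconfirmed, and transient, not drug-related or not judged clinically significant: only the general Grade 3 row remains, so hold and restart.

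The fourth case is the practical reach. (An unconfirmed Grade 4 rise judged unrelated to the drug would match no row, a still rarer corner that the same correction settles.)

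**2. What the ALP sign changes in the more-than-2-of-6 rule.** Drug-related rises count under either sign, because the Section 6.4 list also includes "Any other study drug-related Grade 3 or 4 non-hematologic toxicity". The sign alters the count only for rises that are unconfirmed, accompanied by Grade 2 bilirubin and not drug-related. The documents give no rates, so the following only shows the order of size. Let p be the assumed per-patient rate of other listed toxicity and q the assumed rate of rises whose status depends on the sign. The change is P(X ≥ 3; n = 6, p + q) − P(X ≥ 3; n = 6, p).

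| Assumed p | P(X ≥ 3) at p | Change, q = 0.001 | Change, q = 0.005 |
|---|---|---|---|
| 0.05 | 0.0022 | 0.00013 | 0.00070 |
| 0.10 | 0.0159 | 0.00044 | 0.00228 |
| 0.20 | 0.0989 | 0.00123 | 0.00624 |

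The change is 0.01 to 0.62 percentage points across these assumptions.

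**3. The overlap in Table 1.** Take anemia that is drug-related, clinically significant and unresolved at 48 hours, with Grade 4 unexplained by underlying disease. There are three ways to read the table.

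| Reading | Grade 3 anemia | Grade 4 anemia | Consequence |
|---|---|---|---|
| General Grade 3 row governs Grade 3; hematologic row governs Grade 4 | Hold, restart reduced | Hold, restart reduced | Consistent for anemia, but the last bullet's reference to Grade 3 has no effect |
| Last bullet governs Grade 3; hematologic row governs Grade 4 | Discontinue | Hold, restart reduced | The milder event gets the stricter action |
| Last bullet governs both | Discontinue | Discontinue | Overrides the hematologic row; Grade 4 neutropenia beyond 5 days cannot have resolved by 48 hours, so when drug-related and significant it would never get the restart written for it |

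No reading leaves every row with its stated effect and an ordered set of actions.

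**4. Where the conflict has consequences.** The first restart dose is 0.75 × 800 = 600 mg twice daily and the second is 0.50 × 800 = 400 mg twice daily. Section 6.4 also says: "Patients requiring study drug interruption for more than 3 weeks will be withdrawn from study treatment" (surgery excepted). The two actions therefore differ only for events that last beyond 48 hours and recover in time for a restart within 3 weeks.

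**The case against.** **The sign may be an extraction error.** The Table 1 symbol sits in a broken table, so this is possible, though not the likelier explanation. Checking the PDF is the first step. If the signs agree there, the first half falls away and the second is unaffected.

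**The word "other" already resolves the overlap.** On this view the general Grade 3 row covers only what the table does not list elsewhere, and the narrower last bullet governs. That bullet closely follows the last item of the Section 6.4 list, which supports this. It is a fair reading and removes the double instruction. It is also the second reading above, so it leaves Grade 3 anemia stopped while Grade 4 may restart.

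**A tempting counter-argument fails.** A reader might infer that, because cardiovascular events are carved out of the general Grade 3 row and laboratory events are not, the drafters meant laboratory events to stay there. The text does not establish this. The carve-out removes all Grade 3 cardiovascular, vascular or thrombotic events, whereas the discontinuation bullet covers only drug-related ones, so the carve-out does separate work.

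**There is a practical safeguard.** Table 1 is guidance, there are at most 3 centers, and the medical monitor can be consulted. This limits the harm. However, the clause addresses an investigator who thinks the guidelines should not apply; it does not say which row governs.

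**The anemia evidence is weak on severity.** Phase 1 anemia was reported at any severity, no dose-limiting toxicity occurred from 100 to 1800 mg twice daily, and the animal anemia was mild and recoverable. This stands: the evidence makes the event foreseeable, not frequent.

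**Conclusion.** Both inconsistencies are present as written. They are minor drafting faults in the dosing and safety instructions.

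The ALP reversal is conditional on the symbol being confirmed, and its practical reach is the narrow group in step 1. A reader might infer that it undermines the early safety rule. It does not: drug-related rises count under either sign, and the change is negligible at the assumed rates.

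The laboratory overlap applies only when all three conditions hold (drug-related, clinically significant, unresolved at 48 hours). The choice of row then matters only if recovery allows a restart within 3 weeks. A reader might put an assumed rate on such events and conclude that one among 50 patients is likely or nearly certain. The documents give neither a rate nor the fraction recovering in time, so no magnitude is claimed. Nothing here changes the definition or analysis of ORR, alpha or the sample size.

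**What to change.** 1. Check both ALP symbols against the PDF. If they differ there, use the sponsor's intended direction in both places.
2. Limit the last Table 1 bullet to non-hematologic laboratory toxicity, and add that event (drug-related, clinically significant, unresolved at 48 hours) to the exceptions in the general Grade 3 row.
3. State that hematologic laboratory events follow the hold-and-reduce rows. Word this to include Grade 4 hematologic values the named row omits, such as Grade 4 neutropenia of 5 days or less without fever; otherwise step 2 would leave them without a row.
4. Leave the Section 6.4 toxicity list unchanged, apart from its ALP sign if that is the one in error. Persistent drug-related Grade 3 cytopenia that is clinically significant then still counts toward the early safety rule.

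A simple statement that the last bullet prevails over the general Grade 3 row would be shorter, but it would lock in the stricter action for Grade 3 than for Grade 4 anemia.

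The cost is one symbol and a few words in Table 1, with no added visits, procedures or patients. The downside is clinical: some patients with persistent Grade 3 cytopenia would restart at a reduced dose instead of stopping. The sponsor should confirm that this is acceptable.
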